APPENDIX 4 WOMEN OF CHILDBEARING POTENTIAL DEFINITIONS AND METHODS OF CONTRACEPTION

Appendix 4 provides general information and definitions related to Woman of Childbearing Potential and methods of contraception that can be applied to most clinical trials. For information specific to this study regarding acceptable contraception requirements for female and male participants, refer to [Section 6.1](#) of the protocol. Only the contraception methods as described in Section 6.1 are acceptable for this study.

DEFINITIONS

Woman of Childbearing Potential (WOCBP)

A woman is considered fertile following menarche and until becoming post-menopausal unless permanently sterile. Permanent sterilization methods include hysterectomy, bilateral salpingectomy, and bilateral oophorectomy.

Women in the following categories are not considered WOCBP

- Premenarchal
- Premenopausal female with 1 of the following:
 - Documented hysterectomy
 - Documented bilateral salpingectomy
 - Documented bilateral oophorectomy

Note: Documentation can come from the site personnel's review of the participant's medical records, medical examination, or medical history interview.

- Postmenopausal female
 - A postmenopausal state is defined as 12 months of amenorrhea in a woman over age 45 years in the absence of other biological or physiological causes. In addition, females under the age of 55 years must have a serum follicle stimulating hormone, (FSH) level > 40 mIU/mL to confirm menopause.

Note: Females treated with hormone replacement therapy, (HRT) are likely to have artificially suppressed FSH levels and may require a washout period in order to obtain a physiologic FSH level. The duration of the washout period is a function of the type of HRT used. The duration of the washout period below are suggested guidelines and the investigators should use their judgement in checking serum FSH levels.

- 1 week minimum for vaginal hormonal products (rings, creams, gels)
- 4 week minimum for transdermal products
- 8 week minimum for oral products

Other parenteral products may require washout periods as long as 6 months. If the serum FSH level is > 40 mIU/ml at any time during the washout period, the woman can be considered postmenopausal.

End of Relevant Systemic Exposure

End of relevant systemic exposure is the timepoint where the Investigational Medicinal Product (IMP) or any active major metabolites have decreased to a concentration that is no longer considered to be relevant for human teratogenicity or fetotoxicity. This should be evaluated in context of safety margins from the no-observed-adverse-effect level or the time required for 5 half-lives of the IMP to pass.

METHODS OF CONTRACEPTION

One of the highly effective methods of contraception listed below is required during study duration and until the end of relevant systemic exposure, defined as 5 months after the end of study treatment.*

Local laws and regulations may require use of alternative and/or additional contraception methods.

Highly Effective Contraceptive Methods That Are User Dependent Failure rate of < 1% per year when used consistently and correctly.^a

• Combined (estrogen- and progestogen-containing) hormonal contraception associated with inhibition of ovulation and/or implantation (These methods of contraception cannot be used by WOCBP participants in studies where hormonal contraception is prohibited)^b
– oral (birth control pills)– intravaginal (vaginal birth control suppositories, rings, creams, gels)– transdermal• Combined (estrogen- and progestogen-containing) hormonal contraception must begin at least 30 days prior to initiation of study therapy.

• Progestogen-only hormonal contraception associated with inhibition of ovulation. This method of contraception can only be used by WOCBP participants in studies where hormonal contraception is permitted by the study protocol.^b
– oral– injectable• Progestogen-only hormonal contraception must begin at least 30 days prior to initiation of study therapy.
Highly Effective Methods That Are User Independent

- Implantable progestogen-only hormonal contraception associated with inhibition of ovulation and/or implantation (This method of contraception cannot be used by WOCBP participants in studies where hormonal contraception is prohibited)^b
- Intrauterine device (IUD)^c
- Intrauterine hormone-releasing system (IUS) (This method of contraception cannot be used by WOCBP participants in studies where hormonal contraception is prohibited)^{b,c}
- Bilateral tubal occlusion

- Vasectomized partner

A vasectomized partner is a highly effective contraception method provided that the partner is the sole male sexual partner of the WOCBP and the absence of sperm has been confirmed. If not, an additional highly effective method of contraception should be used.

- Sexual abstinence

Sexual abstinence is considered a highly effective method only if defined as refraining from heterosexual intercourse during the entire period of risk associated with the study treatment. The reliability of sexual abstinence needs to be evaluated in relation to the duration of the study and the preferred and usual lifestyle of the participant.

- Continuous abstinence must begin at least 30 days prior to initiation of study therapy.
- It is not necessary to use any other method of contraception when complete abstinence is elected.
- WOCBP participants who choose complete abstinence must continue to have pregnancy tests, as specified in [Section 2](#).
- Acceptable alternate methods of highly effective contraception must be discussed in the event that the WOCBP participants chooses to forego complete abstinence.
- Periodic abstinence (including, but not limited to: calendar, symptothermal, postovulation methods), withdrawal (coitus interruptus), spermicides only, and lactational amenorrhea method (LAM) are not acceptable methods of contraception for this study.

NOTES:

^a Typical use failure rates may differ from failure rates when contraceptive methods are used consistently and correctly. Use should be consistent with local regulations regarding the use of contraceptive methods for participants participating in clinical studies.

^b Hormonal contraception may be susceptible to interaction with the study treatment, which may reduce the efficacy of the contraceptive method. Hormonal contraception is permissible only when there is sufficient evidence that the IMP and other study medications will not alter hormonal exposures such that contraception would be ineffective or result in increased exposures that could be potentially hazardous. In this case, alternative methods of contraception should be utilized. For information specific to this study regarding permissibility of hormonal contraception, refer to [Sections 6.1 INCLUSION CRITERIA](#) and [7.7.1 PROHIBITED AND/OR RESTRICTED TREATMENTS](#) of the protocol.

^c Intrauterine devices and IUSs are acceptable methods of contraception in the absence of definitive drug interaction studies when hormone exposures from intrauterine devices do not alter contraception effectiveness. For information specific to this study regarding permissibility of hormonal contraception, refer to [Sections 6.1 INCLUSION CRITERIA](#) and [7.7.1 PROHIBITED AND/OR RESTRICTED TREATMENTS](#) of the protocol.

Less Than Highly Effective Contraceptive Methods That Are User Dependent

Failure rate of >1% per year when used consistently and correctly.

- Male or female condom with or without spermicide. Male and female condoms cannot be used simultaneously
- Diaphragm with spermicide
- Cervical cap with spermicide
- Vaginal Sponge with spermicide
- Progestogen-only oral hormonal contraception, where inhibition of ovulation is not the primary mechanism of action (This method of contraception cannot be used by WOCBP participants in studies where hormonal contraception is prohibited)

Unacceptable Methods of Contraception*

- Periodic abstinence (calendar, symptothermal, post-ovulation methods)
- Withdrawal(coitus interruptus)
- Spermicide only
- Lactation amenorrhea method (LAM)

*Local laws and regulations may require use of alternative and/or additional contraception methods.

CONTRACEPTION GUIDANCE FOR MALE PARTICIPANTS WITH PARTNER(S) OF CHILD BEARING POTENTIAL

Male participants with female partners of childbearing potential are eligible to participate if they agree to the following during the treatment and until the end of relevant systemic exposure.

- Inform any and all partner(s) of their participation in a clinical drug study and the need to comply with contraception instructions as directed by the investigator.
- Male participants are required to use a condom for study duration and until end of relevant systemic exposure defined as 7 months after the end of study treatment.
- Female partners of males participating in the study to consider use of effective methods of contraception until the end of relevant systemic exposure, defined as 7 months after the end of study treatment in the male participant.
- Male participants with a pregnant or breastfeeding partner must agree to remain abstinent from penile vaginal intercourse or use a male condom during each episode of penile penetration during the treatment and until 7 months after the end of study treatment.
- Refrain from donating sperm for the duration of the study treatment and until 7 months after the end of study treatment.

COLLECTION OF PREGNANCY INFORMATION

Guidance for collection of Pregnancy Information and outcome of pregnancy on the Pregnancy Surveillance Form is provided in [Section 9.2.6](#) and the Appendix for Adverse Events and Serious Adverse Events Definitions and procedures for Evaluating, Follow-up and Reporting.

APPENDIX 5 ECOG PERFORMANCE STATUS

ECOG PERFORMANCE STATUS^a	
0	Fully active, able to carry on all pre-disease performance without restriction
1	Restricted in physically strenuous activity but ambulatory and able to carry out work of a light or sedentary nature, eg, light house work, office work
2	Ambulatory and capable of all selfcare but unable to carry out any work activities. Up and about more than 50% of waking hours
3	Capable of only limited selfcare, confined to bed or chair more than 50% of waking hours
4	Completely disabled. Cannot carry on any selfcare. Totally confined to bed or chair
5	Dead

^a Oken MM, Creech RH, Tormey DC, Horton J, Davis TE, McFadden ET, and Carbone PP. Toxicity and Response Criteria of the Eastern Cooperative Oncology Group. Am J Clin Oncol 1982; 5: 649-655.

APPENDIX 6 MANAGEMENT ALGORITHMS FOR STUDIES UNDER CTCAE VERSION 5.0

These general guidelines constitute guidance to the Investigator and may be supplemented by discussions with the Medical Monitor representing the Sponsor. The guidance applies to all immuno-oncology agents and regimens.

A general principle is that differential diagnoses should be diligently evaluated according to standard medical practice. Non-inflammatory etiologies should be considered and appropriately treated.

[figure not shown]
Corticosteroids are a primary therapy for immuno-oncology drug-related adverse events. The oral equivalent of the recommended IV doses may be considered for ambulatory patients with low-grade toxicity. The lower bioavailability of oral corticosteroids should be taken into account when switching to the equivalent dose of oral corticosteroids.

Consultation with a medical or surgical specialist, especially prior to an invasive diagnostic or procedure, is recommended.

The frequency and severity of the related adverse events covered by these algorithms will depend on the immuno-oncology agent or regimen being used.

GI Adverse Event Management Algorithm

Rule out non-inflammatory causes. If non-inflammatory cause is identified, treat accordingly and continue I-O therapy.
Opiates/narcotics may mask symptoms of perforation. Infliximab should not be used in cases of perforation or sepsis.

[figure not shown]
Patients on IV steroids may be switched to an equivalent dose of oral corticosteroids (eg, prednisone) at start of tapering or earlier, after sustained clinical improvement is observed. Lower bioavailability of oral corticosteroids should be taken into account when switching to the equivalent dose of oral corticosteroids.

* Discontinue for Grade 4 diarrhea or colitis. For Grade 3 diarrhea or colitis, 1) Nivolumab monotherapy: Nivolumab can be delayed. 2) Nivolumab+ Ipilimumab combination: Ipilimumab should be discontinued while nivolumab can be delayed. Nivolumab monotherapy can be resumed when symptoms improve to Grade 1. Please refer to protocol for dose delay and discontinue criteria for other combinations.

02-Jul-2021

Renal Adverse Event Management Algorithm

Rule out non-inflammatory causes. If non-inflammatory cause, treat accordingly and continue I-O therapy.

[figure not shown]

Patients on IV steroids may be switched to an equivalent dose of oral corticosteroids (eg, prednisone) at start of tapering or earlier, after sustained clinical improvement is observed. Lower bioavailability of oral corticosteroids should be taken into account when switching to the equivalent dose of oral corticosteroids.

02-Jul-2021

Pulmonary Adverse Event Management Algorithm

Rule out non-inflammatory causes. If non-inflammatory cause, treat accordingly and continue I-O therapy.
Evaluate with imaging and pulmonary consultation.

[figure not shown]

Patients on IV steroids may be switched to an equivalent dose of oral corticosteroids (eg, prednisone) at start of tapering or earlier, after sustained clinical improvement is observed. Lower bioavailability of oral corticosteroids should be taken into account when switching to the equivalent dose of oral corticosteroids.

02-Jul-2021

Hepatic Adverse Event Management (For HCC Studies Only)

Rule out non-inflammatory causes. If non-inflammatory cause, treat accordingly and continue I-O therapy.

[figure not shown]

For all participants initiating steroids, consult the BMS Medical Monitor within 24 hours after initiation of steroids, and gastroenterology consult is recommended.

14-Jun-2021

Endocrinopathy Adverse Event Management Algorithm

Rule out non-inflammatory causes. If non-inflammatory cause, treat accordingly and continue I-O therapy.
Consider visual field testing, endocrinology consultation, and imaging.

[figure not shown]

Patients on IV steroids may be switched to an equivalent dose of oral corticosteroids (eg, prednisone) at start of tapering or earlier, after sustained clinical improvement is observed. Lower bioavailability of oral corticosteroids should be taken into account when switching to the equivalent dose of oral corticosteroids.

02-Jul-2021

Skin Adverse Event Management Algorithm

Rule out non-inflammatory causes. If non-inflammatory cause, treat accordingly and continue I-O therapy.

Patients on IV steroids may be switched to an equivalent dose of oral corticosteroids (e.g. prednisone) at start of tapering or earlier, after sustained clinical improvement is observed. Lower bioavailability of oral corticosteroids should be taken into account when switching to the equivalent dose of oral corticosteroids.

[figure not shown]
*Refer to NCI CTCAE v5 for term-specific grading criteria.

^If Steven-Johnson Syndrome (SJS), toxic epidermal necrosis (TEN), Drug Reaction with Eosinophilia and Systemic Symptoms (DRESS) is suspected, withhold I-O therapy and refer patient for specialized care for assessment and treatment. If SJS, TEN, or DRESS is diagnosed, permanently discontinue I-O therapy.

02-Jul-2021

Neurological Adverse Event Management Algorithm

Rule out non-inflammatory causes. If non-inflammatory cause, treat accordingly and continue I-O therapy.

[figure not shown]
Patients on IV steroids may be switched to an equivalent dose of oral corticosteroids (eg. prednisone) at start of tapering or earlier, after sustained clinical improvement is observed. Lower bioavailability of oral corticosteroids should be taken into account when switching to the equivalent dose of oral corticosteroids.

[^]Discontinue for any grade myasthenia gravis, Guillain-Barre syndrome, treatment-related myelitis, or encephalitis.

02-Jul-2021

Myocarditis Adverse Event Management Algorithm

Rule out non-inflammatory causes. If non-inflammatory cause, treat accordingly and continue I-O therapy.

Patients on IV steroids may be switched to an equivalent dose of oral corticosteroids (eg, prednisone) at start of tapering or earlier, after sustained clinical improvement is observed. Lower bioavailability of oral corticosteroids should be taken into account when switching to the equivalent dose of oral corticosteroids. Prophylactic antibiotics should be considered in the setting of ongoing immunosuppression.

02-Jul-2021

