7.4.2 Nivolumab and Ipilimumab Dose Delay Criteria

Dose delay criteria summarized in [Table 7.4.2-1](#) apply for all drug-related AEs, regardless of whether the event is attributed to nivolumab or ipilimumab or both. Delay administration of both nivolumab and ipilimumab if any of the delay criteria in [Table 7.4.2-1](#) are met.

Delay nivolumab and ipilimumab for any AE, laboratory abnormality, or intercurrent illness which, in the judgment of the Investigator, warrants delaying the dose of study medication. Delay study therapy also in cases of confirmed or suspected SARS-CoV-2 infection.

Participants receiving nivolumab plus ipilimumab who have drug-related toxicities that meet the criteria for dose delay should have both drugs (nivolumab and ipilimumab) delayed until retreatment criteria are met, regardless of whether or not the event is attributed to 1 of the drugs. Tumor assessments for all participants should continue as per protocol even if dosing is delayed.

Participants who require delay of nivolumab and ipilimumab should be re-evaluated weekly, or more frequently if clinically indicated, and resume study treatment when re-treatment criteria are met (see [Section 8.1.3](#) [Post Study Treatment Study Follow-up]). Please see also [Appendix 6](#) (IO Management Algorithms) for guidance on appropriate management and follow-up of AEs.

[Table 7.4.2-1](#) summarizes criteria for delaying, resuming, and discontinuing dose of both nivolumab and ipilimumab.

Table 7.4.2-1: Adverse Event Criteria for Delay, Resume, and Discontinue of Nivolumab and Ipilimumab

Drug-Related Adverse Event (AE) per CTCAE V5	Severity	Action Taken	Clarifications, Exceptions, and Resume Criteria
Gastrointestinal			
Colitis or Diarrhea	Grade 2	Delay dose	Dosing may resume when AE resolves to baseline
	Grade 3	Permanently discontinue	
	Grade 4	Permanently discontinue	
Renal			
Serum Creatinine Increased	Grade 2 or 3	Delay dose	Dosing may resume when AE resolves to Grade \leq 1 or baseline value
	Grade 4	Permanently discontinue	
Pulmonary			
Pneumonitis	Grade 2	Delay dose	Dosing may resume after pneumonitis has resolved to \leq Grade 1.
	Grade 3 or 4	Permanently discontinue	
Hepatic			

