8 **DISCONTINUATION CRITERIA**

8.1 **Discontinuation from Study Treatment**

Participants **MUST** discontinue IP (and non-IP at the discretion of the Investigator) for any of the following reasons:

- Participant's request to stop study treatment. Participants who request to discontinue study treatment will remain in the study and must continue to be followed for protocol-specified follow-up procedures. The only exception to this is when a participant specifically withdraws consent for any further contact with him/her or persons previously authorized by the participant to provide this information.
- Any clinical AE, laboratory abnormality, or intercurrent illness which, in the opinion of the Investigator, indicates that continued participation in the study is not in the best interest of the participant.
- Termination of the study by BMS.
- Loss of ability to freely provide consent through imprisonment or involuntarily incarceration for treatment of either a psychiatric or physical (eg, infectious disease) illness. (Note: Under specific circumstances, and only in countries where local regulations permit, a participant who has been imprisoned may be permitted to continue as a participant. Strict conditions apply and BMS approval is required.)
- Criteria listed in [Section 8.1.1](#) (Treatment Discontinuation Criteria).
- Participants meeting progression as assessed by investigator, unless eligible to continue with treatment beyond progression (see [Section 5.1.4](#) [Treatment Beyond Progression]).

- Disease progression or occurrence of a secondary malignancy which requires systemic therapy or radiotherapy for treatment.
- Pregnancy, if locally mandated (see [Appendix 9](#) for country-specific requirements).

Refer to the Schedule of Activities ([Section 2](#)) for data to be collected at the time of treatment discontinuation and follow-up and for any further evaluations that can be completed.

In the case of pregnancy, the Investigator must immediately, within 24 hours of awareness of the pregnancy, notify the BMS Medical Monitor/Clinical Scientist of this event. In most cases, the study treatment will be permanently discontinued in an appropriate manner (eg, dose tapering if necessary for participant safety). Study treatment must be permanently discontinued where locally mandated. See [Section 9.2.6](#) (Pregnancy).

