8.1.1 Treatment Discontinuation Criteria

8.1.1.1 Criteria for Nivolumab and Ipilimumab Treatment Discontinuation

Nivolumab and ipilimumab treatment must be permanently discontinued per criteria in [Table 7.4.2-1](#) in [Section 7.4](#). Discontinue nivolumab and ipilimumab for any adverse event, laboratory abnormality, or intercurrent illness which, in the judgment of the Investigator, presents a substantial clinical risk to the participant with continued nivolumab and ipilimumab dosing. Any event that leads to delay in dosing lasting > 8 weeks from the previous dose requires discontinuation, with the following exceptions:

- Dosing delays to allow for prolonged steroid tapers to manage drug-related AEs are allowed.
- Dosing delays lasting > 8 weeks from the previous dose that occur for non-drug-related reasons may be allowed if approved by the BMS Medical Monitor (or Clinical Scientist).

Tumor assessments should continue as per protocol, even if dosing is delayed. Periodic study visits to assess safety and laboratory studies should also continue Q6W, or more frequently if clinically indicated during such dosing delays.

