8.1.2 Criteria to Resume Treatment

Participants may resume treatment with study drug if they have completed AE management (ie, corticosteroid taper) or are on < 10 mg prednisone or equivalent and meet the requirements per [Table 7.4.2-1](#).

Participants with SARS-CoV-2 infection (either confirmed or suspected) may resume treatment after all of the following conditions are met:

- At least 10 days (20 days for severe/critical illness) have passed since symptoms first appeared or positive test result (eg, reverse transcription-polymerase chain reaction [RT-PCR] or viral antigen), and
- Resolution of acute symptoms (including at least 24 hours have passed since last fever without fever-reducing medications), and
- Evaluation by the Investigator with confirmation that there are no sequelae that would place the participant at a higher risk of receiving investigational treatment

For suspected cases, treatment may also resume if SARS-CoV-2 infection is ruled out and other criteria to resume treatment are met.

When criteria to resume treatment are met, resume both nivolumab and ipilimumab on the same day.

Prior to re-initiating treatment in a participant with a dosing delay lasting > 8 weeks, the BMS Medical Monitor (or designee) must be consulted (see [Section 8.1.1.1](#) [Criteria for Nivolumab and Ipilimumab Treatment Discontinuation]). In addition, see [Appendix 6](#) (IO Management Algorithms) for guidance on appropriate management and follow-up of AEs.

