9 STUDY ASSESSMENTS AND PROCEDURES

- Study procedures and timing are summarized in the Schedule of Activities ([Section 2](#)).

- Protocol waivers or exemptions are not allowed.
- All immediate safety concerns must be discussed with the Sponsor immediately upon occurrence or awareness to determine if the participant should continue or discontinue treatment.
- Adherence to the study design requirements, including those specified in the Schedule of Activities ([Section 2](#)), is essential and required for study conduct.
- All screening evaluations must be completed and reviewed to confirm that potential participants meet all eligibility criteria before randomization. The Investigator will maintain a screening log to record details of all participants screened and to confirm eligibility or record reasons for screening failure, as applicable.
- Procedures conducted as part of the participant's routine clinical management (eg, blood count, baseline scans) and obtained before signing of informed consent may be utilized for screening or baseline purposes, provided the procedure meets the protocol-defined criteria and has been performed within the timeframe defined in the Schedule of Activities ([Section 2](#)).
- Additional measures, including non-study-required laboratory tests, should be performed as clinically indicated or to comply with local regulations. Laboratory toxicities (eg, suspected drug-induced liver enzyme evaluations) will be monitored during the Follow-up Period via on-site/local laboratories until all study drug-related toxicities resolve, return to baseline, or are deemed irreversible.
- If a participant shows pulmonary-related signs (eg, hypoxia, fever) or symptoms (eg, dyspnea, cough, fever) consistent with possible pulmonary AEs, the participant should be immediately evaluated to rule out pulmonary toxicity, according to the suspected pulmonary toxicity management algorithm in the BMS-936558 (nivolumab) IB.¹
- Some of the assessments referred to in this section may not be captured as data in the eCRF. They are intended to be used as safety monitoring by the treating physician. Additional testing or assessments may be performed as clinically necessary or where required by institutional or local regulations.

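### After drug-related Grade 3 diarrhea or colitis, Table 7.4.2-1 stops both drugs for good, but the Appendix 6 GI footnote allows nivolumab to be delayed or resumed alone

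*Combined protocol and SAP*

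**What the plan says.** **Body of the protocol.** Section 7.4.2 introduces Table 7.4.2-1, which "summarizes criteria for delaying, resuming, and discontinuing dose of both nivolumab and ipilimumab". It applies to drug-related events whichever drug is blamed. In the gastrointestinal row for colitis or diarrhea, Grade 2 means delay, with resumption at baseline. Grades 3 and 4 both mean permanent discontinuation, and neither has a resume criterion.

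Three further sections give the table its force:
- Section 8.1 says participants must "discontinue IP (and non-IP at the discretion of the Investigator) for any of the following reasons", and lists the Section 8.1.1 criteria among those reasons.
- Section 8.1.1.1 says "Nivolumab and ipilimumab treatment must be permanently discontinued per criteria in" Table 7.4.2-1.
- Section 8.1.2 lets participants resume if they have completed AE management or "are on < 10 mg prednisone or equivalent and meet the requirements per" the same table. It adds: "When criteria to resume treatment are met, resume both nivolumab and ipilimumab on the same day".

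Section 9 adds: "Protocol waivers or exemptions are not allowed".

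**Appendix 6, GI algorithm footnote.** It discontinues for Grade 4. For nivolumab alone it says: "For Grade 3 diarrhea or colitis, 1) Nivolumab monotherapy: Nivolumab can be delayed". For nivolumab with ipilimumab it says: "Ipilimumab should be discontinued while nivolumab can be delayed. Nivolumab monotherapy can be resumed when symptoms improve to Grade 1". It then refers the reader to the protocol for delay and discontinuation rules in other combinations.

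**The concern.** The same event has two dosing rules. Under the table, a participant with drug-related Grade 3 diarrhea or colitis never receives nivolumab again. Under the footnote, an Arm B participant may have nivolumab delayed, and an Arm A participant may return to nivolumab alone once symptoms reach Grade 1.

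Sections 7.4.2, 8.1.2 and 9.2.10 all direct the treating investigator to Appendix 6. An investigator managing the event can therefore find permission to re-dose without seeing that the table forbids it.

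Enrollment is closed, but Section 5.1 lets participants who tolerate nivolumab with or without ipilimumab continue dosing after unblinding, so the rule can still be applied. The stake is participant safety and consistent handling of a severe toxicity across sites.

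**Working it through.** The plan gives no figure on this point to reproduce. The check is a comparison of texts, followed by a rough sense of scale.

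**1. The two rules side by side (drug-related diarrhea or colitis)**

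| Grade and regimen | Table 7.4.2-1 | Appendix 6 GI footnote | Agree? |
|---|---|---|---|
| Grade 3, nivolumab alone (Arm B) | Discontinue permanently | Nivolumab can be delayed | No |
| Grade 3, combination (Arm A): ipilimumab | Discontinue permanently | Discontinue | Yes |
| Grade 3, combination (Arm A): nivolumab | Discontinue permanently | Delay; resume alone at Grade 1 | No |
| Grade 4 | Discontinue permanently | Discontinue | Yes |

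Section 5.1.2 says the requirements in Sections 7.4 and 8.1.1 apply to participants in any arm, so Arm B falls under the table. Resuming nivolumab alone in Arm A also has no place under Section 8.1.2, which restarts both drugs together.

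**2. Does any text settle which rule wins?**
- *The footnote's own referral.* It sends the reader to the protocol only for combinations other than the two it names. Section 7 says TACE is not a study treatment, so adding TACE does not clearly turn these regimens into other combinations.
- *The override sentence in Section 3.1.2.* It ranks Amendment 01 changes above existing requirements. The Summary of Key Changes shows that Amendment 01 both added Table 7.4.2-1 and updated the Appendix 6 algorithms, so the sentence cannot choose between them.
- *Status of the texts.* Appendix 6 describes itself as guidance; Sections 8.1 and 8.1.1.1 are mandatory. This favours the table, but by inference only.

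**3. Is the whole appendix out of step?** Three Appendix 6 footnotes that state a stopping rule can be read: GI, skin and neurological. Skin (confirmed SJS, TEN or DRESS) and neurological (Guillain-Barré syndrome, myasthenia gravis, treatment-related myelitis or encephalitis) agree with the table. Only GI does not. Most of the flowcharts, including the GI one, are not shown in the public document, so this covers only the readable footnotes.

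**4. Scale**
- Participants on active drug, assuming the 1:1:1 allocation held: 26 × 2/3 = 17.3.
- Low rate: diarrhea was a reason for discontinuation in 2 of 146 HCC participants (Section 3.2.8), or 1.4%, pooled over three schedules, two of them more intensive than the one used here. 17.3 × 2/146 = 0.24 participants.
- High rate: a ceiling of 5% per category for treatment-related Grade 3 and 4 events in NSCLC on the nivolumab Q2W plus ipilimumab Q6W schedule (Section 3.2.7). 17.3 × 0.05 = 0.87 participants. This includes Grade 4, where the two texts agree.
- Cross-check on the same schedule in HCC: discontinuation for AEs of any kind is reported for 1 participant (2.1%, Section 3.2.8) or 2 of 49 (Section 5.4.6).

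**The case against.** The strongest reply is that the hierarchy is already clear. The table is mandatory, waivers are barred, and Section 7.1.1 sends readers to Sections 7.4.2 and 8.1.1.1 for delay and discontinuation. The body cites Appendix 6 for managing and following up events, not for re-dosing. The footnote is also permissive, so an investigator who stops both drugs breaches neither text. This stands as a reason for the table to govern. It does not remove a written permission to do what the table forbids, and it does not supply the missing precedence sentence.

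A second reply is that Appendix 6 is generic: it says it applies to all immuno-oncology agents and regimens. While investigators were blinded to Arm A versus Arm B, they could not have applied the footnote's split between monotherapy and combination. That is fair for the blinded period. Under Amendment 01 the study is unblinded, and the split becomes usable.

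Third, Section 9 requires immediate safety concerns to be discussed with the sponsor to decide whether treatment continues. This safeguard lowers the chance of inconsistent handling, but it does not say which rule the discussion should apply.

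Fourth, the scale figures are loose, and this stands. The 2 of 146 counts discontinuations under another study's rules, not Grade 3 incidence. The 17.3 counts everyone randomized to active drug; those still dosed once Amendment 01 takes effect can be no more than that.

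Finally, the conflict with resuming both drugs together follows largely from the main discrepancy, because that sentence applies only once resume criteria are met and the table gives none here.

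**Conclusion.** The concern holds. For drug-related Grade 3 diarrhea or colitis, current protocol text both forbids and permits further nivolumab in the trial's two active regimens, and nothing in the document states which text prevails. The table is the better-supported rule.

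The discrepancy is confined to nivolumab at Grade 3. It is likely to affect no participant or one: about 0.2 to 0.9 expected events, on the assumption that 1:1:1 allocation put about 17 of 26 on active drug and that the borrowed rates are roughly relevant. No effect on the safety endpoint is claimed. It should be fixed because it is a dosing contradiction after a severe toxicity, however rarely it arises. The GI flowchart is not visible, but the footnote states the permission in full.

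**What to change.** Amend the Appendix 6 GI footnote to say that in CA20974W drug-related Grade 3 diarrhea or colitis requires permanent discontinuation of both nivolumab and ipilimumab, as in Table 7.4.2-1. Add one sentence, in Section 7.4.2 or at the head of Appendix 6, stating that Table 7.4.2-1 governs dosing wherever Appendix 6 differs. When making the change, check the GI flowchart and the other algorithms against the table.

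The cost is one footnote and one sentence, by amendment or clarification letter. No new data or procedures are needed.
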